11.2 Clinical Laboratory Evaluations

Hematology and clinical chemistry will be reported based on the International System of Units (SI). The following laboratory evaluations will be summarized using descriptive statistics:

- Hematology: hematocrit, hemoglobin, mean corpuscular hemoglobin (MCH), mean corpuscular hemoglobin concentration (MCHC), mean corpuscular volume (MCV), platelet count, red blood cell (RBC) count, and white blood cell (WBC) count with differential, reticulocyte count.
- Clinical chemistry: albumin, alkaline phosphatase (ALP), alanine aminotransferase (ALT), aspartate aminotransferase (AST), BUN, calcium, bicarbonate, serum creatinine, creatinine phosphokinase (CPK), glucose, lipase, amylase, phosphate, potassium, sodium, total bilirubin, total cholesterol, total protein, triglycerides, and uric acid. Additionally, the following chemistry parameters collected at Screening only will be included in these outputs: calculated creatinine clearance according to the Cockcroft-Gault equation.
- Urinalysis and microscopy: appearance, occult blood, glucose, leukocyte esterase, nitrite, pH, protein, urobilinogen by dipstick, a reflex microscopic urinalysis will be performed if dipstick protein, nitrite, leukocyte esterase, or occult blood results are positive.

Observed values and changes from screening/baseline, when applicable, for the above laboratory evaluations will be summarized at each visit.

This data will also be summarized in shift tables of baseline to each visit based on range categories of low (below lower limit of normal [LLN], normal, and high [above upper limit of normal [ULN]]).

All laboratory results will be provided in subject data listings. The following additional results will be included in these listings:

- Serology: HIV Ab, HbsAg, HbsAb, and HCV Ab (Screening only).
- Immunology: SARS-CoV-2 (Screening only).
- Pregnancy and FSH Tests: Both urine and serum pregnancy tests will be presented.
- Urine Drug and Alcohol tests: Drug tests will include amphetamine, barbiturates, cocaine, opiates.
- COVID-19: SARS-CoV-2 (Screening only)

Box plots of observed results or change from baseline at each visit for potassium, glucose, lipase, amylase, and creatinine kinase results for each treatment group may be generated.

11.3 Vital Signs

Vital signs will include the following: systolic and diastolic blood pressure (mmHg); heart rate (beats/min), temperature (°C), and respiratory rate (breaths/min).

Observed values and changes from screening/baseline for vital signs will be summarized at each visit and time point. Summaries will be presented by treatment at the time of data collected (i.e., Placebo and CST-2032/CST-107). If multiple collections occur for the same visit and timepoint in two positions, the values will be averaged.

All vital sign data will be listed.

Box plots of observed results or change from baseline at each visit for heart rate, systolic blood pressure, and diastolic blood pressure results for each treatment group may be generated.

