¹ Washout period between Treatment Periods 1 & 2 is 7 to 21 days. The washout period may be extended with prior approval by the CuraSen Medical Monitor,

² Visit to be conducted in the clinic, or other off-site location or at the subject's home according to site preference and capabilities. In addition, should there be factors and/or conditions which would make a site visit unnecessarily difficult and/or potentially unsafe for a subject, some visits and/or procedures may be performed by alternate arrangement, e.g., visits in the subject's home, virtual visits. The End of Study visit is to occur 7-12 days after last dose of study drug.

³ Subjects who withdraw from the study prior to completion of dosing should complete these Day 14 safety assessments at the time of early withdrawal (EW).

⁴ The Color Trails Test should be completed after the CANTAB assessments (select sites only).

⁵ Vital signs to include orthostatic changes in BP and HR, respiratory rate, and oral/tympanic temperature. For assessments of orthostatic changes, BP and HR are obtained: a) after rest in a supine position for at least 5 minutes, and b) 1 minute after standing. Vital signs will be obtained at every study visit as follows:

- Screening
- Day -1 prior to administration of CST-107 or matching placebo in each treatment period
- Days 1, 7, and 14 of each treatment period:
 - Within 30 minutes prior to dosing of study drug (CST-2032+CST-107 or matching placebos),
 - Approximately 4 hours (± 30 minutes) after administration of study drug,

- End-of-Study Visit.

6 ECGs to be obtained in triplicate (separated by approximately 1 minute) after subject is supine for 5 minutes at the following timepoints:

- Screening
- 3 sets of triplicate ECG measures (i.e., 9 ECGs) on Day -1 prior to administration of CST-107 or matching placebo in each treatment period to thoroughly establish a baseline; the time between each set of 3 ECGs should be \leq 5 minutes.
- On Day 1 of each treatment period:
 - Within 30 minutes prior to dosing of study drug,
 - Approximately 1 hour after administration of study drug,
 - Approximately 2 hours after administration of study drug,
 - Approximately 4 hours after administration of study drug,
- Days 7 and 14 of each treatment period:
 - Within 30 minutes prior to dosing study drug,
 - Approximately 1 hour after administration of study drug,
 - Approximately 2 hours after administration of study drug,
 - Approximately 4 hours after administration of study drug,

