5.3. Procedures and Specifications

5.3.1. Medical History, Vital Signs, and Physical Exam

Medical history, including details regarding illnesses and allergies, date(s) of onset, and whether condition(s) is currently ongoing, and medication history, will be collected on all subjects during Screening.

Subject height and body weight will be measured at Screening, and subject's BMI will be calculated and recorded.

Assessment of vital signs will include BP, HR, respiration rate, and oral/tympanic temperature. All routine measures of BP and HR should be collected (a) after rest in a supine position for at least 5 minutes, and (b) 1 minute after standing, to assess orthostatic changes. Vital signs will be collected as indicated in the [Schedule of Events](#).

A complete physical exam will be performed at Screening and will include general appearance and examination of the following body systems (excludes breast, genital, and rectal exams): head, neck and thyroid, eyes, ears, nose, throat, mouth, chest, respiratory, cardiovascular, lymph nodes, abdomen, skin, nails, hair, musculoskeletal, and neurological. A symptom-driven physical exam based on subject complaints will be conducted at the End-of-Study Visit.

5.3.2. 12-Lead ECG

A 12-lead ECG will be collected in triplicate as indicated in the [Schedule of Events](#). Subjects will be required to rest in a supine position for at least 5 minutes prior to the recording of ECG. All ECGs will be reviewed by the Investigator or qualified study staff and will be read by a central reader.

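### SAP 11.3 averages supine and standing vital signs, so the orthostatic BP and HR changes the protocol measures for the primary safety endpoint never reach a treatment-level summary

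*SAP*

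**What the plan says.** The vital-signs footnote (5) to the protocol's Schedule of Events makes orthostatic change part of the assessment: "Vital signs to include orthostatic changes in BP and HR, respiratory rate, and oral/tympanic temperature". It specifies BP and HR "a) after rest in a supine position for at least 5 minutes, and b) 1 minute after standing". Protocol 5.3.1 gives the same two positions and states why both are taken: "b) 1 minute after standing, to assess orthostatic changes". The SAP reproduces footnote 5 in its own Appendix 2.

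Vital signs are named in the primary endpoint in protocol 2.2 and SAP section 3. For analysis, protocol 8.8.3 asks for absolute values and changes from baseline and does not mention combining positions.

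SAP 11.3 lists systolic and diastolic pressure, heart rate, temperature and respiratory rate, without reference to position. It continues: "Observed values and changes from screening/baseline for vital signs will be summarized at each visit and time point". Summaries are by treatment at the time of collection. Then comes the rule at issue: "If multiple collections occur for the same visit and timepoint in two positions, the values will be averaged". The section also says "All vital sign data will be listed" and allows optional box plots of heart rate and blood pressure.

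**The concern.** The protocol takes two readings because their difference is of interest. The SAP replaces them with their mean, which removes that difference, and nothing else in the SAP puts it back. Followed as written, the plan produces no treatment-level orthostatic result for a component of the primary endpoint. The value it does report is neither a supine nor a standing measurement.

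The documents themselves give reasons to want the result. Protocol 1.1.1 lists increased heart rate and peripheral vasodilatation among the known effects of the agonist class, and the agonist is given here with a beta-blocker to subjects aged 50 to 85. The interim vital-signs table marked for the DSMB (14.3.5.1, SAP 4.5) would presumably follow the same rule.

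**Working it through.** The documents state no figure on this point, so there is none to reproduce. The check has three parts.

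**1. Which readings the rule covers.** The protocol schedules BP and HR in two positions only, supine and standing, with no repeat readings within a position. The rule therefore applies to the supine/standing pair. Footnote 5 puts that pair at Screening (1), Day -1 of each period (2), pre-dose and about 4 hours post-dose on Days 1, 7 and 14 of each period (2 × 3 × 2 = 12), and End of Study (1). That is 1 + 2 + 12 + 1 = 16 scheduled timepoints per subject.

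**2. What averaging does.** Let S be the supine value and T the standing value.

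- Value reported under SAP 11.3: A = (S + T)/2, with change from baseline ΔA = (ΔS + ΔT)/2.
- Orthostatic change: O = T − S, with change from baseline ΔO = ΔT − ΔS.

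A does not determine O. If only the standing value falls, by D, then ΔA = −D/2 while ΔO = −D. If ΔS = +10 and ΔT = −10, then ΔA = 0 while ΔO = −20.

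The readings below are assumed, because the documents give none. SBP is in mmHg and HR in bpm.

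| Assumed case | Baseline S/T | Later S/T | A | ΔA | O | ΔO |
|---|---|---|---|---|---|---|
| Standing SBP falls by 10 | 130/130 | 130/120 | 130 → 125 | −5 | 0 → −10 | −10 |
| Standing SBP falls by 20 | 130/130 | 130/110 | 130 → 120 | −10 | 0 → −20 | −20 |
| Standing SBP falls by 30 | 130/130 | 130/100 | 130 → 115 | −15 | 0 → −30 | −30 |
| Both positions fall by 10 | 130/130 | 120/120 | 130 → 120 | −10 | 0 → 0 | 0 |
| Supine rises, standing falls | 130/130 | 140/100 | 130 → 120 | −10 | 0 → −40 | −40 |
| Uneven baseline | 128/126 | 130/110 | 127 → 120 | −7 | −2 → −20 | −18 |
| HR | 65/70 | 60/75 | 67.5 → 67.5 | 0 | 5 → 15 | +10 |

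Rows 2, 4 and 5 all report 120 and a change of −10, with orthostatic changes of −20, 0 and −40. In the HR row the orthostatic rise triples and the reported change is nil.

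**3. A missing standing reading.** The rule operates only when both positions were collected, and SAP 7.4 generally leaves missing data unimputed. A subject with a supine reading alone would then have a single-position value set against a two-position baseline. With the assumed baseline 128/126 (average 127), a supine-only reading of 130 appears as 130 − 127 = +3. The SAP has no rule for this case.

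**The case against.** The strongest reply is that nothing is lost from the database. SAP 11.3 lists all vital-sign data, symptomatic orthostatic events would appear in the adverse event tables by treatment, and protocol section 6 provides for ongoing blinded review of vital signs. The study is descriptive, orthostatic change appears in the collection instructions rather than in the wording of any endpoint, and protocol 8.8.3 asks for no standing-minus-supine summary. The expected effect may also be small. Protocol 1.1.1 reports no clinically significant heart-rate increase and no dizziness at these doses in phase 1, CST-107 is included to attenuate peripheral effects, and early severe autonomic involvement is excluded.

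Part of this stands. The loss lies in the summaries, the changes from baseline and the box plots, and the raw readings should survive by subject. But a listing provides neither a treatment comparison nor a change from baseline, and adverse event tables need not capture orthostatic changes without reported symptoms. For a descriptive safety endpoint the summaries are the result. Protocol 8.8.3 does not call for averaging either, and SAP 2.1, which records changes to the planned analysis, does not mention it. A small expected effect is no reason to use a summary that halves or hides it.

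The sentence might have been intended to cover repeats within one position. It says two positions, however, and the protocol schedules no such repeats. SAP 11.4 describes true repeats differently, as ECG triplicates averaged within a timepoint. Even on that reading, no orthostatic variable is derived.

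**Conclusion.** The concern holds. As written, SAP 11.3 removes the orthostatic comparison from every treatment-level vital-sign summary, in conflict with the protocol's stated purpose and with the footnote in the SAP's own Appendix 2. A standing-only effect is shown at half its size, and opposite supine and standing shifts can cancel completely. The algebra does not depend on the illustrative readings, which are assumptions. Sample size, error rates and randomisation are unaffected. Because vital signs are part of the primary endpoint, this must be corrected before database lock, and before the interim analysis if one is held.

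**What to change.** - Delete the averaging sentence from SAP 11.3 and average only true repeats taken in the same position.
- Summarise supine and standing systolic pressure, diastolic pressure and heart rate separately, by treatment, visit and timepoint, with change from baseline computed within position.
- Derive standing minus supine for each of the three parameters at each timepoint, and summarise it and its change from baseline by treatment.
- Where only one position was recorded, set the difference to missing and report how many subjects lack a standing reading.
- Apply the same layout to interim table 14.3.5.1 and to the optional box plots.
- Optionally, add the number of subjects beyond an orthostatic cut-off. The documents set none, so the choice is the sponsor's.

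The cost is SAP wording, three derived variables and additional table rows. Both the protocol and the SAP sentence itself indicate that readings are taken in two positions. The CRF was not available, so it should be confirmed that position is recorded with each value.

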11.4 Electrocardiogram (ECG)

ECG parameters include: Heart rate, PR interval, RR interval, QRS interval, QT interval, QTcB interval, and QTcF interval. Observed values and changes from baseline for ECG parameters will be summarized at each visit and time point. The baseline measurement may include up to 9 repeat observations, and all repeats will be averaged to obtain a single baseline value. Any ECG parameters taken in triplicate post-baseline will be averaged within timepoint.

Electrocardiograms (ECGs) will be interpreted using the following categories: Normal; Abnormal Not Clinically Significant; and Abnormal, Clinically Significant. Clinical interpretation will also be summarized at each visit and time point.

Additionally, the number and percentage of subjects in each of the following QTcF categories will be tabulated by visit and timepoint:

- $QTcF \leq 450$ msec
- $450 \text{ msec} < QTcF \leq 480$ msec
- $480 \text{ msec} < QTcF \leq 500$ msec
- $QTcF > 500$ msec
- QTcF change from baseline of ≤ 30 msec

- QTcF change from baseline of > 30 msec and ≤ 60 msec
- QTcF change from baseline of > 60 msec

For parameters collected as triplicate measurements, the average of the non-missing measurements will be summarized.

Box plots of observed results or change from baseline at each visit for QTcF pressure results for each treatment group may be generated.

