8.7.1. Analysis of Adverse Events

Safety endpoints will be summarized by disease criteria, treatment, treatment sequence and overall using the Safety Set. Additional summaries may be performed by treatment, treatment sequence and/or period. A limited set of endpoints may also be summarized using other analysis populations.

All reported AEs will be coded using the Medical Dictionary for Regulatory Activities (MedDRA). Adverse event collection will begin during screening and will be collected up to 14 days after the last dose of study drug. All AEs collected on/after first dose of study drug will be considered treatment emergent (TEAE). Each TEAE will further be attributed to a treatment (CST2032+CST-107 or placebo) based on the AE start date. If a TEAE start date is prior to the first dose in Treatment Period 2, the AE will be attributed to the treatment received in Period 1. If a TEAE start date is on/after the first dose in Treatment Period 2, the AE will be attributed to the treatment received in Period 2.

An overall summary of the number and percentage of subjects experiencing TEAEs, serious AEs (SAEs), treatment-related AEs, AEs by maximum severity and AEs leading to treatment withdrawal will be provided. TEAEs, SAEs, and treatment-related AEs will be further summarized by MedDRA system organ class and preferred term and reported by treatment.

All AEs will be listed. Separate listings may be prepared for SAEs, AEs leading to study drug termination, and treatment-related AEs. Individual ECG results will be listed for each subject. Summaries of ECGs by treatment will include observed data and changes from baseline for each parameter including heart rate, QT, and QTcF. The number and percentage of subjects with abnormal ECGs will be summarized by treatment.

Additional analyses may be performed and will be described in the SAP.

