8.8.3. Clinical Laboratory Results, Vital Signs, and ECGs

Absolute values and changes from baseline will be summarized by disease criteria, treatment and overall. In addition, clinical laboratory results, ECG categorical analyses, and ECG shift tables may be generated.

All results will be listed. Laboratory values outside of normal ranges and clinically significant ECG abnormalities will be flagged.

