7.5 Multiple Assessments and Visit Windows

Nominal visits (e.g. those identified by the study CRF) will be the basis of summarization and statistical analysis; no visit date windowing will be conducted. Unscheduled data may be included in summaries of specific abnormalities any time post-baseline and in subject data listings.

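### SAP 11.2 and 11.4 count QTcF categories, ECG interpretation and lab shifts only per visit or timepoint, so the specified tables do not determine how many subjects crossed a threshold on each treatment

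*SAP*

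**What the plan says.** SAP 11.4 defines four absolute QTcF categories and three change-from-baseline categories, and states that "the number and percentage of subjects in each of the following QTcF categories will be tabulated by visit and timepoint". For the reader's normal/abnormal classification it adds: "Clinical interpretation will also be summarized at each visit and time point". SAP 11.2 treats laboratory results alike: "This data will also be summarized in shift tables of baseline to each visit based on range categories".

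Four other provisions bear on the point:

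- Protocol 8.7.1 makes a commitment with no visit qualifier: "The number and percentage of subjects with abnormal ECGs will be summarized by treatment".
- SAP 7.5 makes nominal visits the basis of summaries, then allows an exception: "Unscheduled data may be included in summaries of specific abnormalities any time post-baseline and in subject data listings".
- Protocol 8.8.3 leaves further tables optional: "In addition, clinical laboratory results, ECG categorical analyses, and ECG shift tables may be generated". It also says: "Laboratory values outside of normal ranges and clinically significant ECG abnormalities will be flagged".
- SAP 2.1, which records changes to the planned analysis, does not withdraw the abnormal-ECG count.

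**The concern.** A table by timepoint shows when a drug effect occurs. It does not show how many people had it. Subjects who exceed a limit at different timepoints fall into different cells and are never added together. The same cell totals can also come from a few subjects exceeding repeatedly: a total of 6 may be six subjects once each or two subjects three times each.

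This matters here because ECGs and laboratory safety are named in the primary endpoint (Protocol 2.2), and Protocol 1.1.1 reports QTcF increases and potassium decreases on CST-2032 monotherapy. The same section supports the dose with a statement of the any-time kind: no QTcF above 450 ms and no change above 30 ms in subjects given at least 3 mg nadolol with CST-2032. Unless every cell is zero, the tables in SAP 11.4 would not yield the matching count for this trial.

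**Working it through.** The plan gives no figure to reproduce. The sample size rests on practical grounds, and no rate is stated for any safety threshold. The check is how far the specified tables pin down the number of subjects affected.

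**Step 1. Count the cells per treatment period.** SAP 7.1 sets treatment start at the first dose of CST-2032 or its placebo, so the Day 1 pre-dose readings are not counted. End-of-Study readings come after dosing and are left out.

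- ECG (Schedule of Events, footnote 6): Day 1 at 1, 2 and 4 h; Days 7 and 14 at pre-dose, 1, 2 and 4 h. 3 + 4 + 4 = 11.
- Chemistry (footnotes 19 and 20): about 4 h post-dose on Days 1, 7 and 14. 1 + 1 + 1 = 3.
- Hematology and urinalysis: post-dose on Days 7 and 14 only. 1 + 1 = 2.

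**Step 2. Bound the any-time count A.** With cell counts n_1, ..., n_k among N subjects:

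max(n_j) ≤ A ≤ min(N, Σ n_j)

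Take N = 60 with complete data on each treatment, and one subject in every cell:

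- ECG, 11 cells: A is between 1/60 = 1.7% and 11/60 = 18.3%.
- ECG, only the nine cells at 1, 2 and 4 h: 1/60 = 1.7% to 9/60 = 15.0%.
- Chemistry, 3 cells: 1/60 = 1.7% to 3/60 = 5.0%.
- Hematology, 2 cells: 1/60 = 1.7% to 2/60 = 3.3%.

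**Step 3. Vary an assumed per-cell rate p.** The rates are assumptions. Expected subjects out of 60 are 60p if the same subjects exceed every time, 60[1 − (1 − p)^k] if cells are independent, and 60kp if different subjects exceed each time.

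| Cells k | p | Same subjects (also the count per cell) | Independent | All different |
|---|---|---|---|---|
| 11 (all ECG) | 1% | 0.6 | 6.3 | 6.6 |
| 11 | 2% | 1.2 | 12.0 | 13.2 |
| 11 | 5% | 3.0 | 25.9 | 33.0 |
| 9 (ECG at 1, 2, 4 h) | 2% | 1.2 | 10.0 | 10.8 |
| 3 (chemistry) | 2% | 1.2 | 3.5 | 3.6 |

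Repeated readings in one person are likely to be positively correlated, so a realistic value lies between the first and second results columns. The tables do not say where.

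**Step 4. Look for another specified count.**

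- Protocol 8.7.1 promises one for abnormal ECGs. SAP 11.4 has only the per-timepoint version.
- SAP 7.5 refers to any-time summaries. SAP 11.2 and 11.4 define none, so an unscheduled ECG or laboratory value has no specified table.
- SAP 11.6 does count subjects with C-SSRS events at least once from treatment through follow-up, so this type of count is already in the SAP.

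**The case against.** A reader might infer that the plan never reports how many subjects had an ECG or laboratory abnormality on active versus placebo. The documents do not support that. Protocol 8.7.1 promises an abnormal-ECG count by treatment, and the SAP is to be read with the protocol. SAP 7.5 permits any-time summaries with unscheduled data. Clinically significant laboratory abnormalities are to be recorded as adverse events (Protocol 6.1.2.2), and SAP 11.1 counts subjects with such events by treatment received. Laboratory and ECG results are listed by subject, so the counts can be derived later. No information is lost; the gap is in pre-specification.

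Most of that stands, but it does not close the gap. The adverse-event route depends on investigator judgement, and Protocol 6.2 further asks for symptoms or a change in concomitant therapy. A symptomless QTcF change above 30 ms or a low potassium need not appear there. The provisions in SAP 7.5 and Protocol 8.8.3 are optional and name no table. A count taken from listings would be chosen after unblinding.

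A second tempting reading is that the tables will hide a real signal by a predictable amount. If 6 of 60 subjects each exceeded once at a random one of 11 timepoints, the mean cell would hold 6/11 = 0.55 subjects, and the chance that no cell exceeds 2 would be 0.867. The arithmetic is right, but the 10% rate has no source in the documents. Nor does an even spread fit well: Protocol 1.1.1 says that QTc changes on monotherapy were largest within 4 hours of dosing and gone within a day. Clustering reduces the dilution. With one exceedance at a single post-dose hour on each of the three days, the range is only 1 to 3 subjects.

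**Conclusion.** The point holds as a gap in the specified tables. SAP 11.2 and 11.4 do not determine the subject-level incidence of QTcF exceedance or of low and high laboratory values on active versus placebo, and SAP 11.4 leaves Protocol 8.7.1's abnormal-ECG count without a table.

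The ambiguity is largest for ECGs, up to 11-fold when each cell holds one subject. For chemistry it is at most 3-fold on the same footing. These are bounds, assuming about 60 subjects with complete data on each treatment; they do not predict what the trial will show. If every scheduled cell is zero, the scheduled any-time count is zero too, and only unscheduled values remain open.

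The change is worth making because the affected measures belong to the primary endpoint. It does not call the data collection or the by-timepoint tables into question.

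**What to change.** Add the following to SAP 11.2 and 11.4, by treatment received, with n/N, from scheduled and unscheduled values within each treatment period:

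- each subject's maximum post-baseline QTcF and maximum change from baseline, in the existing categories;
- each subject's worst ECG interpretation, which carries out Protocol 8.7.1;
- each subject's worst post-baseline laboratory shift, at least for low potassium and high glucose.

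Name treatment received as the column, because the SAP 6.1 default for categorical data is disease type, sequence and overall. Keep the by-timepoint tables, which show the time course. A cross-tabulation of active against placebo for subjects with both periods is optional.

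The cost is a few lines of SAP text and one or two more tables from data already collected.
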